10.1.1 Acupuncture Site AESI

Potential adverse events that may occur at the acupuncture site to be documented and followed in this study are:

- Bleeding, Grade ≥ 2 ; (Use “General disorders and administration site conditions, other, specify: “bleeding”)
- Bruising, Grade ≥ 1
- Skin Infection, Grade ≥ 1
- Edema, localized, Grade ≥ 2
- Dry Skin, Grade ≥ 2
- Urticaria (hives), Grade ≥ 1
- Pruritus (itching), Grade ≥ 1
- Rash, maculopapular, Grade ≥ 1
- Pain, Grade ≥ 2
- Flushing, Grade ≥ 2

10.1.2 Other AESI

Other potential adverse events to be documented and followed in this study are noted below. However, these should only be captured if they are deemed **related** to the acupuncture intervention per the Investigator.

- Dizziness, Grade ≥ 2
- Syncope, Grade ≥ 3
- Fatigue, Grade ≥ 2
- Hyperhidrosis, (Sweating) Grade ≥ 2

10.2 Subject Confidentiality

We do not anticipate any breach of confidentiality as no records will be shared with any personnel outside the research team. All medical information including assessments and other medical records will be recorded and stored in a database. The database will exist on a password protected secured server. Medical records data will be abstracted by the Research Designee. All records will be kept confidential.

10.3 Emotional Distress

Some questions in the questionnaires could create emotional distress or confusion. If a subject experiences distress or confusion, the questionnaire process will be interrupted or discontinued, and the Research Designee will follow-up with the Sponsor-Investigator.

10.4 Unanticipated Problems (UAP)

10.4.1 Definition

A UAP is any incidence, experience or outcome that is unexpected (e.g., a lost or stolen laptop computer that contains sensitive study information) given the information provided in research-related documentation (e.g., informed consent) and the study population characteristics, that is related or possibly related to participation in the research study and places the participant at an increased risk.

10.4.2 Reporting

All UAPs occurring during the conduct of a protocol and meeting the definition of a UAP will be reported to the Sponsor-Investigator and IRB per IRB reporting requirements.

11. STATISTICAL CONSIDERATIONS

11.1 Milestones

11.1.1 Registration Date

The date the subject signs the informed consent.

11.1.2 Enrollment Date/On Study Date

The date the subject is randomized.

11.1.3 On Treatment Date

For subjects randomized to the acupuncture arm, the on-treatment date will be the date of the first acupuncture session.

11.1.4 Treatment Discontinuation Date

For subjects randomized to the acupuncture arm, the treatment discontinuation date will be the date the investigator decides to discontinue the subject from receiving acupuncture treatment. See Section 8.1.

11.2 Sample Size

This study is designed with a primary objective to evaluate the effectiveness of acupuncture versus standard subject management in terms of reduction of neuropathy in actively treated multiple myeloma subjects diagnosed with CIPN. A Fisher's Exact Test with a two-sided alpha = 0.20 significance level will have at least 80% power to detect the difference between a standard of care group proportion of 0.10 and a treatment group proportion of 0.35 when the sample sizes are at least 22 and 44 evaluable subjects, respectively. In order to identify at least 66 evaluable subjects, we anticipate enrolling 75 subjects.

11.3 Endpoints

11.3.1 Definition of Primary Endpoint

The primary endpoint for this study is a binary variable that will be determined for each subject indicating whether or not they experienced at least a 2-point improvement in neuropathy between the baseline score and the score obtained at Week 10 (+/- 1 week).

11.3.2 Definition of Secondary Endpoints

- Specific features of CIPN
 - Specific features of CIPN assessed through the NTX subscale from FACT-GOG-NTX will be determined for each subject as a composite measure, which is calculated as the sum of the responses to the NTX subscale questions. For subjects who complete all 12 NTX subscale questions, the composite score will range from 0 to 48.
- Nausea
 - Nausea assessed through question GP2 on the FACT-GOG-NTX subject-reported assessment will be determined for each subject as 5 level ordinal variable from 0 = not at all to 4 = very much.
- Sadness
 - Sadness assessed through question GE1 on the FACT-GOG-NTX subject-reported assessment will be determined for each subject as 5 level ordinal variable from 0 = not at all to 4 = very much.
- Nervousness
 - Nervousness assessed through question GE4 on the FACT-GOG-NTX subject-reported assessment will be determined for each subject as 5 level ordinal variable from 0 = not at all to 4 = very much.
- Sleep quality
 - Sleep quality assessed through question GF5 on the FACT-GOG-NTX subject-reported assessment will be determined for each subject as 5 level ordinal variable from 0 = not at all to 4 = very much.
- Lack of energy
 - Lack of energy assessed through question GP1 on the FACT-GOG-NTX subject-reported assessment will be determined for each subject as 5 level ordinal variable from 0 = not at all to 4 = very much.
- Pain
 - Pain assessed through question GP4 on the FACT-GOG-NTX subject-reported assessment will be determined for each subject as 5 level ordinal variable from 0 = not at all to 4 = very much.
- Constipation
 - Constipation assessed through additional question amended to FACT-GOG-NTX subject-reported assessment will be determined for each subject as a 5-level ordinal variable from 0 = not at all to 4 = very much.
- Dizziness

- Dizziness assessed through additional question amended to FACT-GOG-NTX subject-reported assessment will be determined for each subject as a 5- level ordinal variable from 0 = not at all to 4 = very much.
- Dry Mouth
 - Dry mouth assessed through additional question amended to FACT-GOG-NTX subject-reported assessment will be determined for each subject as a 5- level ordinal variable from 0 = not at all to 4 = very much.
- Quality of Life
 - General Health assessed through CDC-HRQOL Question 1 will be calculated for each subject as a 5- level ordinal variable from Poor to Excellent
 - The number of unhealthy days will be calculated as the average of the number of physically unhealthy days (CDC-HRQOL Question 2) and the number of mentally unhealthy days (CDC-HRQOL Question 3), with a maximum of 30 days.⁷⁴ This will be calculated for each subject as a quantitative value between 0 and 30, representing the number of days out of the past 30 that the subject's health was not good.
 - The number of activity limitation days assessed through CDC-HRQOL Question 4 will be calculated for each subject as a quantitative value between 0 and 30, representing the number of days out of the past 30 that the subject's health kept them from doing their usual activities.

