5.4.4 FACT-GOG-NTX

The validated ⁵⁸ FACT-GOG-NTX questionnaire consists of 39 total items with a 7-day recall period on a 5-point Likert-type scale from 0=*not at all* to 5=*very much*. The questions address CIPN-specific symptoms (e.g., I have numbness or tingling in my hands, I have trouble buttoning buttons), physical well-being (e.g., I have a lack of energy), social/family well-being (e.g., I feel close to my friends), emotional well-being (e.g., I feel sad, I am satisfied with how I am coping with my illness), and functional well-being (e.g., I am able to work including work at home). This questionnaire has been previously used with myeloma patients. ⁶²

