5.4.5 Other Symptoms

The FACT-GOG-NTX covers multiple symptoms of interest (i.e. nausea, sadness, nervousness, sleep quality, lack of energy, and general pain), however there are additional symptoms that will be examined in the current study. To avoid duplication and reduce respondent burden, only those symptoms not covered in the FACT-GOG NTX will be asked about separately. These are constipation, dizziness, and dry mouth. ⁷² These will be assessed with the same 7-day recall period on a 5-point Likert-type scale from 0=*not at all* to 5=*very much* as the FACT-GOG-NTX to make the symptoms comparable. This is a self-created measure of unknown validity.

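### Section 11.3.2 sums the NTX items with no rule for skipped ones, and the item scale is 0 to 5 in Sections 5.4.4 and 5.4.5 but 0 to 4 in Section 11.3.2

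*Combined protocol and SAP*

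**What the plan says.** Section 11.3.2 defines the NTX composite as a measure determined for each subject, "which is calculated as the sum of the responses to the NTX subscale questions". It then gives the range under a condition: "For subjects who complete all 12 NTX subscale questions, the composite score will range from 0 to 48". No range or rule follows for a subject who answers fewer than 12 items.

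The other places where such a rule could stand do not contain one:

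- Section 5.2 lists reasons to record when questionnaire data are missing.
- Section 9.2 has the database checked for omissions and queries raised.
- Section 11.4 makes a subject evaluable on complete baseline and Week 10 neuropathy scores, that is, the 0-10 item. It does not ask for complete NTX items, and it uses this population for all secondary endpoints.
- Section 11.5.5 analyses the composite as continuous, by analysis of variance, and does not mention incomplete forms.

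The item scale is given in two ways. In Section 11.3.2 the nine single-item symptom endpoints are each a "5 level ordinal variable from 0 = not at all to 4 = very much" (with small differences in hyphenation). Section 5.4.5 has the three added items (constipation, dizziness, dry mouth) scored "on a 5-point Likert-type scale from 0=*not at all* to 5=*very much* as the FACT-GOG-NTX to make the symptoms comparable". Section 5.4.4 gives the same 0 and 5 end labels for the FACT-GOG-NTX itself.

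**The concern.** A sum is comparable between subjects only if it runs over the same items. The condition attached to the 0-48 range shows that incomplete forms were foreseen, and the definition still gives every subject a score. Under a literal sum, two subjects with the same symptom severity get different composites if one leaves items blank. The NTX examples in Section 5.4.4 are symptom statements ("I have numbness or tingling in my hands, I have trouble buttoning buttons"), so on raw coding a blank contributes the same as an answer of no symptom.

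This matters because the NTX subscale comes from an instrument that the protocol calls validated, whereas Section 5.4.2 says the validity of the primary 0-10 item is unknown. The composite is therefore natural supporting evidence on neuropathy. The trial is also unblinded (Section 4.1), so a scoring rule left open until the data are seen could be chosen with the arms known.

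The scale conflict is a separate matter. Someone building or checking a form from Section 5.4 could allow a top code of 5, for which the endpoint definitions have no level.

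**Working it through.** **Inputs from the documents.** 12 NTX items, a sum score and a stated range of 0 to 48 (Section 11.3.2); item codes 0 to 4 (Section 11.3.2) or 0 to 5 (Sections 5.4.4 and 5.4.5).

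**Assumptions, not in the documents.** A mean item response of 2; per-item skip rates m of 1%, 2% and 5%; skipping independent across items where stated.

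**Step 1: reproduce the stated range.** Maximum = items x top code.

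- Codes 0 to 4: 12 x 4 = 48, which matches Section 11.3.2.
- Codes 0 to 5: 12 x 5 = 60, which does not.
- Codes 0 to 5 are six values, so the 5-point description in Sections 5.4.4 and 5.4.5 also disagrees with its own end labels. Codes 0 to 4 are five values.

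**Step 2: literal sum with k items skipped.** Highest possible score = 4 x (12 - k). At a mean response of 2, plain sum = 2 x (12 - k), against 24 for a complete form. Prorated score = plain sum x 12 / (12 - k).

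| k skipped | Highest possible | Plain sum | Shortfall from 24 | Prorated |
|---|---|---|---|---|
| 1 | 44 | 22 | 2 (8%) | 24 |
| 2 | 40 | 20 | 4 (17%) | 24 |
| 3 | 36 | 18 | 6 (25%) | 24 |
| 6 | 24 | 12 | 12 (50%) | 24 |

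**Step 3: average shortfall in an arm.** Shortfall = 12 x m x 2.

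- m = 1%: 12 x 0.01 x 2 = 0.24 points
- m = 2%: 12 x 0.02 x 2 = 0.48 points
- m = 5%: 12 x 0.05 x 2 = 1.2 points

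**Step 4: effect on the arm difference.** With equal skip rates and similar mean responses the shortfalls largely cancel. With unequal rates the spurious difference is the difference between the shortfalls: 0.48 - 0.24 = 0.24 points for 2% against 1%, and 1.2 - 0.24 = 0.96 points for 5% against 1%.

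**Step 5: share of forms with at least one gap, assuming independence.** 1 - (1 - m)^12 = 11.4%, 21.5% and 46.0% for m = 1%, 2% and 5%. So a low item-level rate can still leave many forms without a defined full-range score, although the average loss in points is small.

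**The case against.** The strongest reply is that Section 11.3.2 never says that partial forms are summed over the answered items or that a skip is scored 0. It defines a sum and gives the range for complete forms. The FACT-GOG-NTX is cited as a published instrument, and its own scoring may be what was intended. This stands in part: summing what was answered is the literal consequence of the only rule given, not an explicit instruction. But the plan does not invoke any external scoring rule, and it says that a composite is determined for each subject.

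The direction of the error is also not settled. A reader might infer that a skipped item must look like improvement. That holds only if items are summed raw, as written. Reverse scoring, which the documents do not mention, would flip the direction. Section 11.5.5 does not specify a change score either.

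A reader might also infer that skipping will differ between arms because one arm attends for acupuncture. The documents do not support this. Sections 5.1 and 5.4 offer paper, electronic and, if needed, phone completion to all subjects, chosen by circumstances and preference. Section 9.2's check for omissions may recover some blanks, though it is not a scoring rule.

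On the scale, the 5-point wording, the nine 0 to 4 definitions and the 48-point range all agree, so the top label of 5 looks like a slip. Nor is Section 5.4.5 the only specification of the three added items, because Section 11.3.2 defines them too. For the single-item endpoints the analysis is on ranks, so five options with the top one coded 5 instead of 4 would change nothing. That protection does not extend to the NTX composite, which is a sum, or to a form that offers six options.

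**Conclusion.** The point holds in a limited form. The plan has no rule for partly answered NTX forms, and the rule it does give, applied literally, puts them on a shorter scale. The scale conflict is explicit in current text, and the internal evidence favours 0 to 4.

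The likely size is modest. Under the stated assumptions the average shortfall is 0.24 to 1.2 points on a 48-point scale, and most of it cancels if both arms skip equally. For an individual form the loss is larger: 2 points per skipped item at a mean response of 2. The documents give no skip rates, so the actual effect on the arm comparison cannot be computed.

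It would be wrong to read this as a threat to the main result. The primary endpoint is a single 0-10 item, and neither it nor the sample size depends on NTX scoring. The change is still worth making before analysis, because it is cheap and removes a choice that would otherwise be made with the data in view.

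**What to change.** **Section 11.3.2.** Score the NTX composite as (sum of answered items x 12) / (number of items answered) when a prespecified minimum is answered, and set it to missing otherwise. More than half, that is at least 7 of 12, is one reasonable threshold. The documents do not supply one; what matters is that it is fixed in advance. Every scored subject then stays on the 0-48 range. State in the same place whether items are summed raw or reversed, and whether a higher composite is better or worse.

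**Sections 5.4.4 and 5.4.5.** Change the scale to 0 = not at all to 4 = very much, in line with Section 11.3.2.

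**Forms.** Check that the paper, electronic and phone versions in use, including the three added items, offer five options coded 0 to 4.

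**Cost.** A few sentences of protocol wording and a check of the form coding. The small downside is that prorating assumes the answered items represent the skipped ones.

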11.3.3 Definition of Safety Endpoints

- Adverse Events of Special Interest will be determined for each subject as binary variables indicating whether or not they experienced an AESI. These will be determined by preferred term, system organ class, and overall.

11.3.4 Definition of Exploratory Endpoints

- Opioid use
 - Opioid use assessed through Morphine Equivalent Daily Dose (MEDD) will be calculated for each subject as a quantitative value.
- Concomitant medication use
 - Concomitant medication use assessed through medication name and dose will be determined for each subject.
- Acupuncture administration
 - Acupuncture administration will be defined for each subject on the acupuncture arm as the number of attended acupuncture sessions from 0 to 12.
- Acupuncture expectancy
 - The acupuncture expectancy score will be captured quantitatively for each subject as a composite score ranging from 4 to 20.

11.4 Analysis Populations

The intent to treat (ITT) population will consist of all randomized subjects. The ITT population will be used to summarize the CONSORT diagram, subject disposition, and baseline subject disease characteristics. The evaluable population will consist of enrolled subjects who have complete baseline and Week 10 (\pm 1 weeks) neuropathy scores. The evaluable population will be

used for the analyses of all primary and secondary endpoints. Additionally, an intervention-compliant population will be defined as all subjects in the evaluable population who meet all of the following criteria:

- Subjects randomized to the acupuncture arm who have received at least 75%, or 9 of the 12 sessions in up to 13 weeks from randomization.
- Subjects randomized to the control arm who have not received any acupuncture at any time while they are on study.

The intervention-compliant population will be utilized for sensitivity analyses.

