4. SUBJECT ALLOCATION

4.1 Randomization

Subjects will be randomized in a 2:1 fashion to either acupuncture plus standard subject management or standard of care alone and assigned a Sequence Number. This will be accomplished utilizing the CTMS, whereby a list of Sequence Numbers and associated treatment arm assignments randomly generated prior to study activation will be uploaded by a member of the Levine Cancer Institute Biostatistics Core. The Sequence Number will be a four digit, randomly generated ID number, ranging from 0001 to 9999. A stratified block randomization will be utilized including the following stratification factors to reduce confounding of comparisons between the treatment arms:

- Baseline neuropathy score (neuropathy score 2 – 6 vs 7 – 10)

Blinding will not be possible within this trial because the subjects and study personnel will be able to decipher intervention from control based on the study activities. Those exposed to acupuncture will understand that they are in the intervention group and those given standard of care only will understand that they are in the control group. If a subject in the control group has an acupuncture session while enrolled, they will be discontinued from the study and all further assessments at that point.

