Subjects in both the treatment arm and the control arm will complete the study questionnaires at protocol defined timepoints, even if bortezomib/bortezomib-combination therapy is removed from their treatment regimen during the study (for those on active treatment). Questionnaires should be completed at protocol defined timepoints even if those on the acupuncture arm have not received the acupuncture session on schedule or if sessions are missed.

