6. STUDY CALENDAR

Procedures/Assessments	Screening Visit	Baseline (complete within 2 weeks from consent, can be done at screening AFTER Randomization)	Weeks 1-2 ² : Twice per week	Weeks 3-10 ² : Once per week	Week 5 ± 1 week ^{3,5} Midpoint	Week 10 ± 1 week ^{3,5} Endpoint	Early Termination (if applicable) ⁷	Follow Up (30 days [+7] from last Acup tx)
Informed Consent Form	X							
Randomization via CTMS (within 2 weeks from consent)		X ¹²						
Sociodemographics & Medical History (see 5.3.1 and 5.3.2)		X						
Multiple Myeloma status ⁶		X						
ECOG	X							
Height / Weight/ BMI		X						
Acupuncture Expectancy Scale ⁴		X ⁴						
Acupuncture Treatment ^{1,2}			X ²	X ²				
Collect Chemotherapy regimen information ¹⁰	X					X	X	
Adverse Events of Special Interest ⁸			Continuously, starting at First Acupuncture session			X	X ¹³	
CIPN: Neuropathy 0-10 & neuropathy physical location	X ¹¹				X	X	X	
CIPN: FACT-GOG-NTX		X ¹⁴			X	X	X	
Other Symptoms: Constipation, dizziness, dry mouth		X ¹⁴			X	X	X	
Quality of Life: CDC HRQOL-4		X ¹⁴			X	X	X	
Opioid Intake/ Morphine Equivalent Daily Dose (see Appendix B)		X ⁹			X	X	X	
Concomitant Medication: (See Section 5.3.4 for which medications to collect)		X ⁹			X	X	X	

Key to Footnotes

¹ First acupuncture session to occur within 2 weeks of enrollment (date randomized). Acupuncture treatment schedule to start on a Monday or Thursday only.

² Week 1 for subjects on the acupuncture/intervention arm is the week when the first acupuncture session occurs. Window for acupuncture sessions during Week 1 and Week 2 is at least 1 day (minimum) and no more than 8 days (maximum) between visits. Window for sessions during Weeks 3-10 is at least 2 days (minimum) and no more than 9 days (maximum) between visits. During Week 1 and Week 2, if an acupuncture session is missed, it may be made up the following week (there will be 3 sessions that following week). During Weeks 3-10, no sessions will be made up if missed.

³ Questionnaires at Midpoint and Endpoint should still be collected even if subject decides to discontinue the acupuncture sessions but is willing to stay on study. Week 1 for the control group begins at Randomization.

⁴ Acupuncture Expectancy Scale questionnaire to be collected only from subjects on Intervention (Acupuncture) arm at any time AFTER Randomization has occurred, but PRIOR to first acupuncture session.

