⁵ For acupuncture arm, Midpoint occurs at Week 5 ± 1 week from first acupuncture session, with Endpoint occurring at Week 10 ± 1 week from first acupuncture session. For control arm, Midpoint occurs at Week 5 ± 1 week from Randomization with Endpoint occurring at Week 10 ± 1 week from Randomization.

⁶ Collect MM date of diagnosis and staging at Baseline

⁷ If a subject decides or needs to be withdrawn from the study early (all visits and acupuncture assessments, if applicable), but is willing to complete an Early Termination visit, subject will complete assessments a final time, and will be considered Off Study (See section 8.2). Subjects do not need to complete questionnaires if they have done so within the last 2 weeks.

⁸ AESIs should only be collected on subjects randomized to acupuncture arm, beginning with first acupuncture session until 30 days after final acupuncture session.

⁹ For collection of opioid medication intake and concomitant medications, collect what has been taken over the past 7 days.

¹⁰ Collect chemotherapy regimen information throughout the study (if applicable).

¹¹ CIPN Neuropathy 0-10 & neuropathy physical location questionnaire is to be completed the first time **after consenting and prior to any other baseline procedures or assessments** to determine if the subject qualifies for enrollment into the study (see section 7.1.1).

¹² Notify subject of their randomization result.

¹³ Follow Up on AESIs: Can be done over the phone- this follow up for AESIs is only for subjects randomized to Acupuncture treatment arm.

¹⁴ Questionnaire may be completed after consent and prior to or after Randomization

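### No primary or secondary efficacy analysis covers all randomised subjects, and Section 4.1 requires outcome loss for control subjects who have acupuncture

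*Combined protocol and SAP*

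**What the plan says.** Section 11.4 sets up three populations.

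- Intention-to-treat, all randomised: "The ITT population will be used to summarize the CONSORT diagram, subject disposition, and baseline subject disease characteristics". No efficacy use is given.
- Evaluable: "The evaluable population will consist of enrolled subjects who have complete baseline and Week 10" (±1 week) neuropathy scores. This set is "used for the analyses of all primary and secondary endpoints".
- Intervention-compliant, a subset of the evaluable set and the only one named for sensitivity analyses. Its control criterion is "Subjects randomized to the control arm who have not received any acupuncture at any time while they are on study".

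Section 5.2 records why questionnaires are missing, but nothing in Section 11 uses those reasons or says how a missing Week 10 score is handled.

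Follow-up after a departure from assigned treatment differs by arm. Under Section 4.1, a control subject who "has an acupuncture session while enrolled, they will be discontinued from the study and all further assessments at that point". Section 8.2 confirms that Off Study subjects give no further data. For the acupuncture arm, Section 5.1 says "Questionnaires should be completed at protocol defined timepoints even if those on the acupuncture arm have not received the acupuncture session on schedule", and Section 6, footnote 3, says "Questionnaires at Midpoint and Endpoint should still be collected even if subject decides to discontinue the acupuncture sessions", provided the subject stays on study. Section 8.1 calls such subjects Off Treatment, not Off Study. Removal for non-compliance or by investigator decision (Section 8.2) is discretionary and applies to both arms.

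**The concern.** The trial is open-label and the endpoint is self-reported, so whether a Week 10 score exists may depend on both arm and outcome. If it does, the groups compared are no longer the groups that were randomised. Controls who seek acupuncture may well be those who are not improving, and removing them makes the remaining control arm look better. Dissatisfied acupuncture subjects who leave would push the comparison the other way. If loss is unrelated to outcome, there is no bias.

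The plan has no analysis that would show which of these happened. Continuing accrual until 66 subjects are evaluable (Section 11.5.1) replaces numbers but not comparability. An imputation analysis can be added later, but a control score that was never collected cannot be recovered.

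**Working it through.** **1. The plan's own figures.** Inputs from Section 11.2: two-sided Fisher test at 0.20, rates 0.10 and 0.35, 22 and 44 evaluable, 75 enrolled. Allocation is 2:1 (Section 4.1). Power is the sum, over all improver counts x of 22 and y of 44, of Bin(x; 22, 0.10) × Bin(y; 44, 0.35) wherever the Fisher p-value is at most 0.20. The result is 0.817, which agrees with the stated 80% or more. Expected loss is 75 − 66 = 9, and 9/75 = 12%. Spread 2:1, that is 6 of 50 acupuncture and 3 of 25 control subjects.

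**2. Passages that do not fit together.**

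- Section 4.1 stops all assessments for an exposed control. Section 7.1.2 asks for questionnaires in both arms whether or not acupuncture was received, though this may have been meant for missed sessions.
- Section 6, footnote 7 ("If a subject decides or needs to be withdrawn from the study early") offers an Early Termination visit that Section 4.1 appears to bar. A score taken before Week 9 would not make the subject evaluable in any case.
- If Section 4.1 is followed, the control criterion of the compliant set excludes almost nobody. It still covers acupuncture at or after the Week 10 score.

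**3. Removal of non-improving controls, no true effect.** Assumptions: 75 fixed (50:25), 12% random loss in the acupuncture arm, a fraction d of non-improving controls removed, no other control loss. The evaluable control rate is p / [p + (1 − p)(1 − d)].

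- p = 0.30, d = 0.20: 0.30 / (0.30 + 0.70 × 0.80) = 0.30/0.86 = 0.349, so the bias is 0.30 − 0.349 = −0.049.
- p = 0.10, d = 0.20: 0.10 / (0.10 + 0.90 × 0.80) = 0.10/0.82 = 0.122, so the bias is −0.022.

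Rejection probabilities come from exact enumeration over evaluable numbers and improvers in each arm:

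| d | p = 0.30: against acupuncture | p = 0.30: for | p = 0.10: against | p = 0.10: for |
|---|---|---|---|---|
| 0% | 0.087 | 0.078 | 0.083 | 0.053 |
| 10% | 0.119 | 0.054 | 0.096 | 0.044 |
| 20% | 0.162 | 0.035 | 0.127 | 0.032 |
| 30% | 0.219 | 0.020 | 0.169 | 0.022 |

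Simulated accrual to 66 evaluable does not cure this. At p = 0.30, results against acupuncture are 0.08, 0.12, 0.16 and 0.23 (20,000 trials each, blocks of 3 assumed).

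**4. Loss in the other direction, no true effect.** If 25% of non-improving acupuncture subjects are lost, false wins are 0.19 (p = 0.30) or 0.11 (p = 0.10). At the planned 12% loss, with acupuncture losses all non-improvers and control losses random, they are 0.14 or 0.076. Without informative loss at 44 v 22 they are 0.077 or 0.052.

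**5. Power at 0.35 v 0.10.** Under the assumptions of step 3, with 0, 10 or 20% of non-improving controls removed, power is 0.85, 0.79 or 0.71.

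**6. Tipping point at the planned loss.** Six acupuncture and three control scores can be filled in 7 × 4 = 28 ways.

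- Observed 15/44 v 2/22 (p = 0.037): p ≤ 0.20 in favour of acupuncture holds in 24 of 28. The worst case is 15/50 v 5/25, p = 0.42.
- Observed 11/44 v 2/22 (p = 0.191), the narrowest win at 2/22: it holds in 13 of 28.

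**7. What an analysis can repair.** These are simulated biases in the rate difference (6,000 trials, 20 imputations, true rate 0.30, 20% of non-improving controls lost; SD 2 and correlation 0.6 assumed):

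| Loss depends on | Completers | Multiple imputation | Missing = not improved |
|---|---|---|---|
| Week 5 score | −0.019 | −0.002 | +0.025 |
| Week 10 score | −0.050 | −0.038 | 0.00 |

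Imputation repairs the first kind of loss but not the second.

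**The case against.** The strongest reply is about weight. The documents give no crossover rate, and nothing suggests that acupuncture among controls would be common. The Section 4.1 rule costs an outcome only if the session comes before the Week 10 score. The 20% scenario removes 25 × 0.70 × 0.20 = 3.5 or 25 × 0.90 × 0.20 = 4.5 controls, all non-improvers, while the plan implies about 3 control losses from every cause. Only the 10% scenario is near that.

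Total two-sided error also stays within 0.20 in most cells: at most 0.169 + 0.022 = 0.191 at the plan's own control rate, and 0.162 + 0.035 = 0.197 at rate 0.30 with 20% removed. Only 30% removal at the assumed rate of 0.30 exceeds it (0.219 + 0.020 = 0.239). The result at the planned effect survives 24 of 28 completions, and any borderline result is fragile. Section 7.1.2 can be read as covering missed sessions only. Week 5 neuropathy is not a listed secondary endpoint, so its population is arguably unstated rather than restricted.

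These points stand as limits on size. They do not supply the missing analysis. The total error rate also hides the shift in direction: results against acupuncture exceed 0.10 on that side in five of the six removal cells. And the lack of an all-randomised sensitivity analysis does not depend on crossover, because the plan itself expects nine subjects without a usable outcome.

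**Conclusion.** The concern holds. Section 11.4 leaves every randomised subject without a Week 10 score out of all primary and secondary efficacy analyses, and no sensitivity analysis brings them back. Sections 4.1 and 8.2 make outcome loss mandatory for controls who have acupuncture before that score. In the acupuncture arm, loss after departure from treatment is only possible.

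The size cannot be fixed from the documents. At the plan's 0.10 rate, removing 10 to 20% of non-improving controls raises false results against acupuncture from 0.083 to between 0.096 and 0.127, and lowers power from 0.85 to between 0.79 and 0.71. Informative loss in the acupuncture arm at the planned 12% raises false wins from 0.052 to 0.076 at rate 0.10, or from 0.077 to 0.14 at rate 0.30. The removal fractions, the 0.30 rate and the loss by arm are assumptions. The sample-size calculation is correct. This should be fixed, but it does not invalidate the design.

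**What to change.** 1. Reconcile Section 4.1 with Section 7.1.2, Section 6 footnote 7 and Section 11.4, so that Midpoint and Endpoint questionnaires continue for control subjects who have acupuncture. Record the exposure and exclude these subjects only from the intervention-compliant set. This concerns data collection only. If acupuncture has no effect, it restores the 0% row of the table in step 3.
2. Keep the Fisher test by assigned arm on observed Week 10 scores as primary; it then includes these controls. Pre-specify two sensitivity analyses in all randomised subjects: multiple imputation of the 0–10 score from arm, baseline, Week 5 and Early Termination scores, from which the 2-point improvement is derived; and a tipping-point analysis, since imputation does not repair loss that depends on the Week 10 score. Show missing = not improved only beside these, because it can favour acupuncture when control loss is higher.
3. State that the Week 5 and repeated-measures analyses (Section 11.5.5) use all available Week 5 scores. As the secondary analyses are now worded, the natural reading drops subjects who have a Week 5 but no Week 10 score.
4. Keep 66 evaluable subjects as the trigger for the analysis.

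The cost is wording in Sections 4.1, 11.4 and 11.5, a few more questionnaires and some analysis time. There is one statistical price: retained controls may improve after acupuncture and narrow the difference. If 20% of non-improving controls have acupuncture and 0, 10 or 28% of them then improve, the control rate is 0.10 + 0.90 × 0.20 × (0, 0.10 or 0.28) = 0.100, 0.118 or 0.150. Power with 75 fixed is then 0.85, 0.785 or 0.66, against 0.71 if they are removed.
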